## I. BACKGROUND AND SIGNIFICANCE

Restless Legs Syndrome (RLS) is a sensory-motor neurological disorder characterized by an irresistible urge to move the legs that is often paired with leg discomfort. Symptoms are provoked by rest, relieved with movement, and worst in the evening or at night. Clinically significant RLS that occurs at least two times per week, and is associated with moderate to severe distress, is present in roughly 3% of the general population. Such sufferers describe these leg sensations on a spectrum from annoying to unbearable and the physical distress and lack of sleep associated with RLS contribute to high levels of morbidity and poor quality of life.

Sleep disturbance is present in over 75% of individuals with RLS, producing most of the morbidity of moderate to severe RLS, and is the primary complaint which drives individuals with RLS to seek medical attention. RLS is associated with difficulty falling asleep, repeated awakenings, and total sleep times averaging less than 5.5 hours. Both the sensory discomfort as well as the periodic limb movements of sleep (PLMS) are thought to contribute to RLS sleep disturbance.

Dopamine agonists (DAs) have been the mainstay of medical treatment for 20 years and remain first-line therapy for many patients. Most patients with RLS initially experience prompt suppression of the sensory symptoms upon treatment with a DA. Alpha-2-delta agents such as gabapentin and pregabalin are also used in RLS treatment with substantial benefit for the sensory symptoms.

Unfortunately, persistent difficulties with all phases of sleep are common in patients whose RLS symptoms are resolved with treatment. Meta-analyses of DA clinical trials in RLS demonstrate that the absolute effect size (as change from baseline) is only .4 when compared to placebo. These small to moderate effects of DAs leave the average treated RLS patient with sleep durations of just over 6 hours. Alpha-2-deltas also leave effectively treated RLS patients with persistent insomnia, with average sleep latencies over 30 minutes, WASO of 60-90 minutes, and sleep efficiencies of 75-85%. Similarly, iron treatments, which often produce substantial benefits for RLS symptoms, do not produce any improvement for sleep in clinical trials. In community surveys of treated RLS patients, 53% report sleep disruption four or more nights per week.

Multiple potential causes for treatment-refractory sleep disturbance exist, including activating effects of DAs, conditioned insomnia and poor sleep habits as a result of chronic RLS-related sleep disturbance, and comorbid medical and psychiatric illness. Another potential explanation is the suggestion from emerging data that RLS and insomnia share genetic underpinnings and thus may be comorbid independent of any prior sensory symptoms.

In the absence of any clinical trials addressing the issue, the persistent insomnia in patients with effectively treated RLS is currently addressed empirically with FDA-approved (benzodiazepine receptor agonists) and non-approved (trazodone) agents, with varying success. Use of the former category risks the emergence of complex sleep-related behaviors, which occur at higher rates in RLS, whereas the latter risks worsening the underlying RLS. Gabapentin is sometimes attempted as a hypnotic in such patients though its side-effect profile may worsen underlying gait instability in older patients. Cognitive-behavioral treatment of insomnia (CBT-I) is generally efficacious for chronic insomnia and is first-line treatment for this disorder. However, as the sleep deprivation initially produced by CBT-I is known to exacerbate RLS severity, this approach is generally not used in RLS.

Suvorexant provides an important therapeutic option to treat insomnia in the context of RLS. It has demonstrated long-term efficacy, particularly in shortening the duration of nocturnal awakenings and increasing total sleep time. Similarly, it has a comparatively benign side effect profile compared to many of the agents described above.

Orexin is thought to play a key role in the central regulation of arousal which accounts for its benefits in insomnia. RLS, like insomnia, has been associated with hyperarousal. Whether orexin plays a specific role in RLS-related sleep disturbance is unclear. Two previous studies have examined orexin levels in RLS patients, with conflicting results.

To summarize, the proposed study is not to treat RLS but rather to address the substantial proportion of RLS patients whose core RLS symptoms are effectively managed by medications but are left with persistent insomnia. Clinically significant RLS is present in 3% of adults, roughly one-half of whom have control of core RLS symptoms with treatment. Over half of these patients report persistent insomnia, even with substantial control of their RLS symptoms, due to the limitations of current RLS medications. Thus, roughly 0.5-1% of adults have persistent insomnia with effectively treated RLS. Existing insomnia treatments can either worsen underlying RLS or lead to complex sleep-related behaviors or other side effects in this primarily older population. Suvorexant provides a potentially important option due to its efficacy and tolerability profile.

## **II. SPECIFIC AIMS**

## Primary Aim:

• To determine whether suvorexant will have significantly greater effect than placebo in increasing actigraphically-derived total sleep time (TST) in patients with effectively treated restless legs syndrome (RLS) with persistent insomnia.

## Secondary Aims:

- To determine whether suvorexant will have significantly greater effect than placebo in reducing actigraphically-derived wake after sleep onset (WASO) in patients with effectively treated RLS with persistent insomnia.
- To determine whether suvorexant will have significantly greater effect than placebo in decreasing Insomnia Severity Index (ISI) scores in patients with effectively treated RLS with persistent insomnia.

## **Exploratory Aims:**

- To determine whether suvorexant will have significantly greater effect than placebo for self-reported sleep metrics (e.g., quality, disturbance, sleep latency and duration) in patients with effectively treated RLS with persistent insomnia.
- To determine whether suvorexant will have an effect on RLS severity in patients with effectively treated RLS with persistent insomnia.

# **III. SUBJECT SELECTION**

The following lists the inclusion/exclusion criteria for prospective participants.

# **Inclusion Criteria:**

- 1. Men or women of any ethnic origin
- 2. Written informed consent is obtained
- 3. Speaks and writes in English
- 4. A willingness and ability to comply with study procedures.
- 5. Age 18 years or older
- 6. Diagnosis of RLS via Cambridge-Hopkins RLS questionnaire
- 7. International Restless Legs Syndrome Study Group scale score (IRLS)<15

8. RLS treatment with a dopaminergic agonist, an alpha-2-delta agent, iron, cannabinoids, or an opioid\*

- 9. No changes in RLS medication in the previous month
- 10. DSM-5 criteria for Insomnia Disorder

11. Report a total sleep time  $\leq$  7 hours and wake after sleep onset > 45 minutes on 7 or more of the 14 nightly sleep logs during both the initial 2-week screening period and the two-week screening run-in period. WASO does not decrease by more than 50% on the 2-week sleep diary obtained between the screening visit and the randomization visit.

\*If patient is using an opioid to treat their RLS, the following additional exclusion criteria will apply:

- 1. Individuals taking opioids at an MME > 40 MME daily (e.g., oxycodone > 26 mg, methadone > 10 mg)
- 2. Individuals taking opioids who have comorbid conditions accompanied by significant hypoxia, hypercapnia, or decreased respiratory reserve such as: severe asthma, chronic obstructive pulmonary disease, or severe obesity

- 3. Individuals taking opioids at any dose with concurrent gabapentin, pregabalin or gabapentin enacarbil
- 4. Individuals who have changed their opioid dose within the past 6 weeks

## **Exclusion Criteria:**

1. Sleep and medical factors:

a. Diagnosis of moderate/severe obstructive sleep apnea (AHI>30) not using CPAP (can be included if CPAP adherent), or other untreated primary sleep disorders (e.g. narcolepsy)b. Shift workers

c. Unwillingness to not use sedative-hypnotics (other than suvorexant) during the study period

d. Unwillingness to maintain stable RLS medication during the study unless medically indicated

e. Current use of an opiate medication.

f. Unwillingness to not take stimulants (e.g. caffeine) after 4:00 pm during the study.

2. Psychiatric factors:

a. Current major depressive episode, by report and as indicated by the Patient Health Questionnaire  $(PHQ-9)^{26}$ 

- b. Lifetime history of bipolar disorder, psychosis, or other serious psychiatric illness
- c. Current alcohol/substance use disorder
- 3. Medical factors:
  - a. BMI  $\geq 40 \ kg/m^2$
  - b. Renal or hepatic disease judged to interfere with drug metabolism and excretion
  - c. Pregnancy or breastfeeding
  - d. Malignancy within past 2 years
  - e. Surgery within past 3 months

f. Neurological disorder or cardiovascular disease raising safety concerns about use of suvorexant and/or judged to interfere with ability to assess efficacy of the treatment

- g. Medical instability considered to interfere with study procedures
- h. Concomitant medications with drug interaction or co-administration concerns
- i. Contraindications or allergic responses to suvorexant
- j. History of being treated with suvorexant
- 4. Lifestyle and other factors:
  - a. Travel across two time-zones during the week prior to enrollment
  - b. Greater than 6 cups of coffee per day

# **Exclusionary Medications**

The following medications are considered exclusionary:

- Strong inhibitors of CYP3A (e.g., ketoconazole, itraconazole, posaconazole, clarithromycin, nefazodone, ritonavir, saquinavir, nelfinavir, indinavir, boceprevir, telaprevir, telithromycin, conivaptan)
- \*Maximum dose of 10 mg will be considered for subjects taking: moderate CYP3A inhibitors (e.g., amprenavir, aprepitant, atazanavir, ciprofloxacin, diltiazem, erythromycin, fluconazole, fosamprenavir, grapefruit juice, imatinib, verapamil)
  - In certain cases, subjects on moderate CYP3A inhibitors may be administered 20 mg of suvorexant if the study doctor determines that side effects at 10 mg do not preclude an increase in dose. In these events, an additional safety phone call will be performed after 1 week at the higher dose (20 mg) in both treatment periods, in which it will be determined whether the subject should stay at 20 mg or decrease back to 10 mg.

## **IV. SUBJECT RECRUITMENT AND ENROLLMENT**

## Methods of recruitment and procedures for informed consent:

The target enrollment for the study is N=90 individuals with treated RLS and insomnia. Potential subjects will be informed of the study in one of five ways: 1) through advertisements on the Partners Clinical Trials webpage, 2) through advertisements on Facebook, Google, and Reddit, 3) through referral by a providing clinician, 4) through the RSVP for Health, or 5) through letters/announcements via Patient Gateway. Patients will be identified using RPDR and Epic. We will only send targeted letters and announcements to patients with a diagnosis of RLS.

The enrollment goal for effectively treated RLS with persistent insomnia will be addressed by specifically targeting sleep clinics at Massachusetts General and Brigham and Women's Hospital, as well as the HMS-affiliated Beth Israel Deaconess Hospital, for all of which the PI teaches and supervises Fellows in sleep clinics. The PI has close ties to many clinicians in these clinics, and they have conveyed their interest in recruiting for this study given the high prevalence of insomnia in this population.

Interested patients may contact the study staff using the contact information provided in the advertisements or by the research coordinator/clinician (in the form of a small handout). During initial phone contact with MGH staff, interest in the study will be re-confirmed and verbal informed consent will be obtained, after which a phone screen will be conducted by a member of the study staff.

The potential risk of coercion for study subjects will be managed by ensuring that their treating physician provides only a study handout to potential study participants. Potentially eligible patients may separately contact a research coordinator to further inquire about participation. Once the subject has agreed to participate, the MGH study physician will participate in the consenting

procedures to ensure that any questions regarding the study are answered accurately and to the fullest extent possible.

Interested subjects will provide verbal consent at the time of the initial phone call, at which time they will be informed that their data will be used to study the effect of suvorexant on sleep disturbance in people with treated RLS. Verbally consented subjects will be assigned a unique identifier that will be used to link screening questionnaire data to the subject's record.

Verbally consented subjects will be re-consented during the Screening Visit. Written consent will be obtained by the study physician using a written Informed Consent Form including a summary of HIPAA policies; the signatures on the Informed Consent Form will be obtained electronically (via the REDCap e-consent framework). A signed copy will be given to the subject. Once consent is obtained, patients will be assigned a new unique identifier, which will be used to link all questionnaire data with the patient's record throughout the study. The questionnaire data linked with each unique identifier will be collected and stored on REDCap (Research Electronic Data Capture), which is a secure, HIPAA compliant web-based application and database hosted by Partners HealthCare. A separate database at the Sleep Disorders Clinical Research Program at Massachusetts General Hospital will contain personal identification data.

If subjects have questions concerning their rights as a research subject, they may call the Human Subjects Committee office at MGH, or speak with study clinicians. All study documents will be stored electronically in REDCap as well as encrypted laboratory computers, and access to this information will only be given to the research personnel.

## Study Design and projected enrollment:

This is a two-arm, double-blind, randomized placebo-controlled crossover 2.5-month trial, investigating the effects of suvorexant 10–20 mg on actigraphically-derived total sleep time in patients with persistent insomnia and effectively treated RLS.

All study procedures will be conducted at Massachusetts General Hospital. Based on experience from our research group in patients with insomnia and RLS, we expect to consent and evaluate for eligibility up to 90 patients in order to achieve our projected randomized sample size of 44 patients with effectively treated RLS, who will be randomized in a 1:1 ratio to suvorexant 10–20 mg or equivalent placebo for four weeks followed by crossover (after a 2 week washout) to the alternate treatment. Our goal is to have 34 patients with effectively treated RLS complete the trial with evaluable data at 2.5 months, after allowing for post-randomization drop-outs.

We expect that many of the participants in this study will have numerous other health conditions which are thought to place them at higher risk of COVID-19-related complications. Thus, considering the safety and mental wellbeing of our subjects, all study visits will occur remotely.

For the remote visits, research staff will follow the MGB requirements for using the appropriate virtual tools. The study physician will remain on call during all points of remote visits in case there any emergent medical or psychiatric issues.

## **V. OVERVIEW OF STUDY PROCEDURES**

### Visit 1: TELEPHONE SCREEN (WEEK -4)

An initial screen will be conducted over the phone, consisting of a brief clinical and sleep history for inclusion and exclusion criteria. If preliminary eligibility appears adequate and the individual expresses interest, they will be sent links to complete the following questionnaires on REDCap:

- 1) the Insomnia Severity Index to assess insomnia severity
- 2) the PHQ-9 to screen for depression
- 3) the IRLS to assess RLS severity
- 4) the STOP-BANG questionnaire to screen for sleep apnea
- 5) an electronic 14-day sleep diary

Upon our review of these completed surveys and diaries, those who meet further eligibility criteria, as determined by the diaries (see Inclusion and Exclusion Criteria above), will be scheduled for a Screening Visit.

## Visit 2: SCREENING VISIT (WEEK -2)

Written informed consent will be obtained by the study doctor at the Screening Visit for the remaining screening procedures and all treatment-related procedures (via the IRB-approved Informed Consent Form via the REDCap e-consent framework). Risks and benefits associated with use of suvorexant will be described. At that time, further eligibility will be assessed with a clinical interview conducted by a sleep medicine-trained psychiatrist to diagnose chronic insomnia disorder and to ensure that contraindicated sleep, medical and psychiatric problems and medications are excluded. Urine screens for pregnancy will be performed at an affiliated site; the study physician will order these tests.

Phillips Actiwatch Spectrum Plus actiwatches will be mailed to participants, and returned by mail to investigators, at the outset and the end, respectively, of the screening run-in. Actigraphy baseline data will be collected during the 14 days of the screening run-in period. Actiwatches will be worn on the non-dominant wrist both day and night at all times except when showering. Standardized operating procedures developed by the Actigraphy Core of the Division of Sleep Medicine at MGH will be followed. Event marker button press will establish "lights out" and "lights on" and will be compared with the daily diary times and adjusted if necessary, using written protocols. Sleep onset

and offset times will be computed using the vendor provided software by a trained technician supervised by the consultant ([name], the Core Chief). The following key standard actigraphy metrics will be generated on each day's data: Sleep onset, sleep offset, time in bed (TIB), total sleep time (TST), sleep latency, wake after sleep onset (WASO), sleep efficiency and naps.

Screening Run-In: They will receive daily email links to an online sleep diary to complete on 14 consecutive days during the screening run-in period.

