## Visit 3: BEGIN FIRST TREATMENT (WEEK 0)

At this Randomization Visit, the 2-week sleep diary will be reviewed for definitive eligibility before the participant is randomized to treatment. Baseline questionnaires will be determined at this visit. Baseline subjective and actigraphic sleep measures will be determined from the last 7 days of this 2-week period. Baseline pre-treatment symptom measures will be determined from the Randomization Visit. If the subject did not wear the actiwatch over 80% of the time during the two weeks before randomization, or if their data is missing (e.g. due to device malfunction), the actigraph will be sent back to the subject and he or she will be asked to repeat the baseline data collection period.

Eligible participants will be randomized in a 1:1 ratio for the first 4-week period of placebo or suvorexant. Subjects will be mailed 14 days of the 10 mg dose of study medication following this visit.

Subjects will also be mailed 42 additional pills of the 10 mg dose for use in weeks 1 to 3. Subjects will also be mailed actiwatches, and will be instructed to wear these during the two weeks leading up to Visit 5.

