### Visit 6: BEGIN SECOND TREATMENT (WEEK 6)

After the 2-week washout phase all participants will be crossed over to the other treatment for the second 4-week treatment phase. Subjects will be mailed 14 days of the 10 mg dose of either suvorexant or placebo following this visit.

Subjects will also be mailed 42 additional pills of the 10 mg dose for use in weeks 7 to 9. Subjects will also be mailed actiwatches, and will be instructed to wear these during the two weeks leading up to Visit 8.

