#### **Table of Procedures:**

		Screening Period		Treatment Period 1			Treatment Period 2		
Visit		V1/ Initial Screening	V2/ Screening	V3/ Randomization	V4/ Interim phone Contact 1	V5/ End of 1st Treatment	V6/ Begin 2nd Treatment	V7/ Interim phone Contact 1	V8/ End of 2nd Treatment
Study Week		-4	-2	0	1	4	6	7	10
Visit Location		Phone	Zoom	Zoom	Phone	Zoom	Zoom	Phone	zOOM
General/ Screening Assessment	Sleep/medical/mental health phone screening and verbal consent	x							
	Written Informed Consent		x						
	Eligibility Criteria		x	x					
	Medical History		x						
	Urine hCG		x						
	Concomitant Medication		x	x	x	x	x	x	x
	ISI	x		x		x			x
	PHQ-9	x							
	STOP-BANG	x							
	CH-RLSq		x						
	BDI			x		x			x
	IRLS	x		x		x			x
	CGI-I					x			x
	PGI-I					x			x
	DBAS			x					
Sleep Assessment	Sleep Diaries (administer/review)	xª		xb		xb			xb
	Actigraphy (administer/download)			xb		xb			xb
	PSQI			x		x			x
Dispensing of Actiwatches in mail	Given to subject		x		x			x	
	Returned by subjects			x		x			x
Medication Dispensed in Mail				x	x		x	x	
Safety Assessment/ Adverse Event Reporting					x	x		x	x
Medication Adherence					x	x		x	x
Study procedures completed between study events: a = daily for 2 wks following visit, b = daily for 2 wks prior to visit									

hCG = Human chorionic gonadotropin, ISI = Insomnia Severity Index, PHQ-9 = Patient Health Questionnaire, CH-RLSq = Cambridge-Hopkins RLS questionnaire, BDI = Beck Depression Inventory, IRLS = International Restless Legs Scale, CGI-I = Clinician Global Impression of Improvement, PGI-I = Patient Global Impression of Improvement, DBAS = Dysfunctional Beliefs and Attitudes about Sleep, PSQI = Pittsburgh Sleep Quality Index.

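### The single pregnancy test is scheduled at Week -2, and nothing requires a recent negative result before the first study drug is mailed (minor; period 1 entry only)

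*Combined protocol and SAP*

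**What the plan says.** Section III, Exclusion Criteria, item 3c, excludes "Pregnancy or breastfeeding". Section V, Visit 2 (Week -2), provides for the test: "Urine screens for pregnancy will be performed at an affiliated site; the study physician will order these tests". It gives no collection date, window or repeat. In the Table of Procedures the urine hCG row has one mark, under V2.

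The same table marks "Eligibility Criteria" at both V2 and V3. At Visit 3 (Week 0), "Eligible participants will be randomized in a 1:1 ratio for the first 4-week period of placebo or suvorexant". The one item that the Visit 3 text names for the final eligibility decision is the two-week sleep diary. If actiwatch wear is too low or data are missing, "he or she will be asked to repeat the baseline data collection period". The actiwatch is "returned by mail to investigators, at the outset and the end, respectively, of the screening run-in", so a decision to repeat can come only after the device is back.

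Drug goes out after randomisation: "Subjects will be mailed 14 days of the 10 mg dose of study medication following this visit". For period 2 the plan says "Subjects will be mailed 14 days of the 10 mg dose of either suvorexant or placebo following this visit", with no further hCG marked.

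**The concern.** The test that supports exclusion 3c comes at the start of a two-week drug-free interval, although the exposure it guards against begins at the end of that interval. A participant who conceives during the run-in, or whose pregnancy is too early to detect at V2, would have a valid negative on file. She could be randomised and sent drug without any departure from the plan. A repeated baseline lengthens the gap, and nothing renews the test. All visits are remote.

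What is at stake is safety at entry to period 1: dosing someone the protocol means to exclude. The documents give no figure for fetal risk, so the point rests on the protocol's own exclusion. Sample size, type I error and the primary analysis are not affected.

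**Working it through.** **Inputs from the protocol.** V2 is Week -2, V3 is Week 0 and V6 is Week 6. The run-in lasts 14 days. 44 participants are randomised 1:1. The hCG is marked once, at V2.

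**Inputs not given, assumed for illustration.** Actiwatch return and review before a repeat, r = 3 to 10 days. Time from V3 to first dose, m = 1 to 5 days. Limit on test age at V3, w = 7 days.

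**Nominal interval.** (0 − (−2)) × 7 = 14 days, which agrees with the stated run-in.

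**Age of the result at V3.** Let s be the number of days after V2 on which the sample is taken.

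- Single baseline: 14 − s. A sample at V2 (s = 0) gives 14 days; a sample on the last day (s = 14) gives 0.
- Baseline repeated once, sample in the first run-in: 14 + r + 14 − s = 28 + r − s. With s = 0 this is 28 days before any return time is counted, and 31 to 38 with r = 3 to 10.

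So 14 and 28 + r are upper values for a test done at V2. They are not ages that the plan guarantees.

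**Age at first dose, sample at V2.** Single baseline: 14 + m = 15 to 19 days. Repeated baseline: from 31 + 1 = 32 to 38 + 5 = 43 days. These ranges depend on the assumed r and m.

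**With the proposed change.** A sample taken before V3 is at most w = 7 days old at V3, and at most 7 + m = 8 to 12 days old at first dose. A repeated baseline does not change this, because the test then falls at the end of the repeated period. A sample taken after V3 is as old at first dose as test turnaround plus postage, neither of which is given.

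**Start of period 2.** A test done at V2 is (6 − (−2)) × 7 = 56 days old at V6, or 56 + 14 = 70 nominally with a repeated baseline. With the change it is at most 42 + 7 = 49. In the placebo-first sequence, 44 / 2 = 22 participants first receive suvorexant after V6. The change therefore mainly serves the other 22.

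**The case against.** The strongest reply is that this is an ordinary design choice. One screening test about two weeks before randomisation breaks no rule in the documents, and nothing in them says that 14 days is too old or 7 days is right. The collection date is open: V2 is held remotely and the sample is taken elsewhere, so a site could already collect late in the run-in. The eligibility mark at V3 covers all criteria, including 3c, so a known or suspected pregnancy would stop entry. The Background describes the patients as mainly older. Re-timing also gives up early detection and leaves the larger gap at V6.

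Much of this stands. It limits the point to an unrecognised pregnancy, in probably few people, and makes the day counts upper nominal values. It does not supply a rule that the result on file at V3 be recent. Entry is open to women from age 18, and the sponsor already judged a test necessary.

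Three stronger readings are tempting and are not supported:

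- A reader might infer that pregnancy is not checked at randomisation, or that the sections contradict each other. The V3 eligibility mark rules that out: a positive V2 result would stop entry.
- A reader might infer that results will be 14 or 28 days old. The plan does not fix the sampling date.
- A reader might infer that contraception or pregnancy-reporting instructions are missing. Consent pages were removed before review, so their absence here shows nothing.

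**Conclusion.** The point holds as a minor, inexpensive safety improvement for entry to period 1. The schedule allows a result up to 14 days old at randomisation, or 28 or more with a repeated baseline after a test at V2, and no section requires a recent negative before drug is mailed. The number of participants able to become pregnant is not given, so the number at risk cannot be estimated; it is likely to be small. The conclusion needs only the visit weeks, the single hCG mark and the repeat rule. The longer day ranges and the 7-day limit rest on stated assumptions. Nothing here threatens the trial's result.

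**What to change.** Keep one test per participant able to become pregnant, still ordered at V2, but collect it in the last 7 days of the run-in or between V3 and the first mailing. Two edits suffice:

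- **Table of Procedures:** move the urine hCG mark from V2 to V3, with a footnote: collected within 7 days before V3, or before mailing.
- **Section V, Visit 3:** add: *For participants able to become pregnant, the first study medication will be mailed only after a negative urine hCG collected no more than 7 days before V3, or between V3 and mailing, is recorded; if the baseline is repeated, the test is taken at the end of the repeated period.*

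The Visit 2 sentence can stay, since it says who orders the test and where it is done but not when. No study drug is given between V2 and V3, so the later test loses no protection.

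Costs and limits:

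- A pregnancy may be found only after most of the run-in is complete.
- A few participants with a repeated baseline may need a second test.
- Very early pregnancies can still be missed.
- A test left until after V3 may delay mailing. A positive result at that stage leaves a randomised participant without a dose, and Statistical Methods keeps such participants out of the primary analysis. Collection before V3 is therefore preferable.
- The V6 start of period 2 remains covered only by this earlier test. A repeat before the V6 mailing would be an added procedure for the sponsor to weigh separately.
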